#### **5.6.5. Surgery**

There are no known effects of idelalisib or ofatumumab on coagulation or wound healing. Pending receipt of additional information and considering the subject's current platelet counts, idelalisib may be continued in the peri-procedural period in subjects who require surgery or invasive procedures.

#### **5.7. Duration of Study Drug**

Subjects may continue receiving idelalisib until the occurrence of any events requiring study drug discontinuation as defined in Section 5.8.

Subjects may continue to receive ofatumumab until the earliest of a maximum of 12 infusions or the occurrence of any events requiring study drug discontinuation as defined in Section 5.8.

***Note: Subjects in Arm A will continue receiving idelalisib or ofatumumab, even if the other drug must be discontinued due to toxicity.***

#### **5.8. Discontinuation of Study Drug**

All study participants may receive idelalisib indefinitely and may receive ofatumumab through 12 infusions. However:

- Any subject has the right to discontinue study drug at any time.
- Any subject who has objective evidence of definitive CLL progression (confirmed by IRC) will discontinue study drug.
- Any subject unable to tolerate a second rechallenge with protocol-described, dose-modified idelalisib at Dose Level –1 (100 mg BID) (see Section 5.3.4) should discontinue idelalisib.
- Any subject who becomes pregnant or begins breastfeeding should discontinue study drug.
- Any subject who becomes significantly noncompliant with study drug administration, study procedures, or study requirements should discontinue study drug.
- The investigator may discontinue study drug, if it is not in the subject's best interest to continue.
- Any subject who is diagnosed with any grade of SJS, TEN, PJP, or organizing pneumonia, or any subject diagnosed with Grade  $\geq 2$  pneumonitis should discontinue study drug.
- Any subject whose benefit-risk profile is not deemed positive by the investigator should discontinue study drug.

If allowed by local regulations, Gilead Sciences may transition subjects from study drug to commercial drug supply when idelalisib becomes commercially available in the country where the subject is living.

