Grade 3 (ALT/AST>5-20xULN) (Bilirubin>3-10xULN)	Withhold idelalisib. Monitor ALT, AST, ALP, and bilirubin at least 1x per week until all abnormalities are Grade ≤ 1. If bilirubin abnormality was Grade < 3, resume idelalisib at same dose level. If bilirubin abnormality was Grade ≥ 3, resume idelalisib at lower dose level.	Delay ofatumumab as necessary to ensure subject is sufficiently stable to receive further treatment; thereafter maintain full dose and schedule.
Grade 4 (ALT/AST>20xULN) (Bilirubin>10xULN)	Withhold idelalisib. Monitor ALT, AST, ALP, and bilirubin at least 1x per week until all abnormalities are Grade ≤ 1. If bilirubin abnormality was Grade < 4, resume idelalisib at lower dose level. If bilirubin abnormality was Grade 4, discontinue idelalisib.	Delay ofatumumab as necessary to ensure subject is sufficiently stable to receive further treatment; thereafter maintain full dose and schedule.
Pneumonitis (with new onset or worsening of baseline, dyspnea, cough, or hypoxia without obvious infectious cause)		
Grade 1 (asymptomatic)	Withhold idelalisib until resolution to baseline. May resume at lower dose level or discontinue study drug at investigator discretion.	Maintain current dose level and schedule.
Grade ≥ 2	Discontinue idelalisib permanently in subjects with any severity of symptomatic pneumonitis and institute therapy as clinically appropriate.	Delay ofatumumab as necessary to ensure subject is sufficiently stable to receive further treatment; thereafter maintain full dose and schedule.
Other Nonhematological Adverse Events		
Grade ≤ 2	Maintain current dose level and schedule	Maintain current dose level and schedule.
Grade ≥ 3	Withhold idelalisib until Grade ≤ 1. May resume idelalisib at initial or lower dose level or discontinue idelalisib at investigator discretion.	Delay ofatumumab as necessary to ensure subject is sufficiently stable to receive further treatment; thereafter maintain full dose and schedule or discontinue ofatumumab at investigator discretion.
Pneumocystis jirovecii pneumonia (PJP)		
Any Grade	Discontinue idelalisib permanently	

NCI CTCAE Grade	Recommendations and Required Action (in italics)	
	Idelalisib	Ofatumumab
Organizing Pneumonia		
Any Grade	Discontinue idelalisib permanently	
CMV infection/reactivation		

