### 5.4.3. Gastrointestinal Events

Isolated cases of gastrointestinal inflammation (eg, stomatitis, colitis, cecitis) have been noted in subjects receiving idelalisib. Rare cases of gastrointestinal perforation have occurred, generally in the setting of occult carcinoma, mesenteric embolus or diverticular disease. Study treatment (idelalisib) **must** be discontinued in subjects who experience bowel perforation.

Cholangitis manifest as hyperbilirubinemia out of proportion to serum transaminase elevations has been observed. While disease-related factors, neutropenia, toxicity from prior therapies, effects of ongoing supportive care, or pre-existing cholelithiasis may have initiated such events, it is possible that idelalisib played a contributory role. In such subjects, rechallenge with idelalisib has been possible and has not been associated with other severe adverse events. Subjects who have developed evidence of enteritis during idelalisib therapy have been successfully treated with antidiarrheals (eg, loperamide) and with enteric steroidal (eg, budesonide) or non-steroidal (eg sulfasalazine [[Azulfidine®](#)]) anti-inflammatory agents and have been able to continue or resume idelalisib.

For study subjects who develop severe abdominal pain the possibility of a bowel obstruction or perforation should be considered. Appropriate clinical and radiographic examination should be performed and supportive care or surgical intervention should be considered. Upon recovery, ofatumumab may be resumed.

For subjects who develop persistent diarrhea, causes related to concomitant medications or gastrointestinal infections such as *Clostridium difficile* (particularly for patients recently treated with broad spectrum antibiotics), *Shigella*, *Campylobacter*, *Yersinia* and CMV should be considered and treated if appropriate. Depending upon the clinical circumstances, endoscopy and biopsy, with bacterial and viral IHC staining should be considered. In the event that an infectious

cause is not identified, an antimotility agent (eg, loperamide) may lessen symptoms and intervention with enteric steroidal (eg, budesonide) or non-steroidal (eg, sulfasalazine) anti-inflammatory agents should be considered. In such subjects, rechallenge with idelalisib at a lower dose level has resulted in recurrence of symptoms in some but not all subjects and has not been associated with other severe adverse events.

[figure not shown]

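### After Grade ≥2 pneumonitis, Protocol Sections 5.7 and 5.8 end ofatumumab while Table 5-4 continues it, because *study drug* has no fixed meaning

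*Protocol*

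**What the plan says.** **Section 5.7 (Duration of Study Drug).** "Subjects may continue to receive ofatumumab until the earliest of a maximum of 12 infusions or the occurrence of any events requiring study drug discontinuation", these events being those defined in Section 5.8. A note in the same section adds: "Subjects in Arm A will continue receiving idelalisib or ofatumumab, even if the other drug must be discontinued due to toxicity".

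**Section 5.8 (Discontinuation of Study Drug).** One bullet reads "Any subject who is diagnosed with any grade of SJS, TEN, PJP, or organizing pneumonia, or any subject diagnosed with Grade" ≥2 "pneumonitis should discontinue study drug". It is not limited to one drug or one arm. The bullet on failed rechallenge in the same list does name a single drug: such a subject "should discontinue idelalisib".

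**Section 5.3.4, Table 5-4.** For Grade ≥2 pneumonitis the idelalisib column requires permanent discontinuation. The ofatumumab column says: "Delay ofatumumab as necessary to ensure subject is sufficiently stable to receive further treatment; thereafter maintain full dose and schedule". For PJP and organizing pneumonia of any grade the table stops idelalisib permanently and shows no ofatumumab instruction in the text as read. For SJS/TEN it stops idelalisib and interrupts coadministered medications that may be associated with these reactions, without saying whether ofatumumab is one of them.

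**Sections 5.4.2 and 5.4.9.** For SJS/TEN, Grade ≥2 pneumonitis and organizing pneumonia, the drug named for discontinuation is idelalisib.

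**The concern.** A stopping rule for a serious lung event should give one answer for each drug. Here a site that starts from Sections 5.7 and 5.8 ends ofatumumab after Grade ≥2 pneumonitis, and a site that starts from the ofatumumab column of Table 5-4 resumes it. The difference is sharpest in Arm B, where ofatumumab is the only drug: one passage ends all study treatment and the other does not.

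Subject safety is at stake first, since the protocol describes pneumonitis and organizing pneumonia that required ventilation or were fatal (Section 8.5.1.4). Ofatumumab exposure also depends on the passage followed. So do the counts in the planned summary of adverse events leading to discontinuation of idelalisib or ofatumumab (Section 9.4.2.4).

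**Working it through.** The plan gives no figure to reproduce. The check sets the passages side by side and then counts the infusions that depend on the choice.

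**1. Ofatumumab after each event**

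| Event | Sections 5.7 + 5.8 | Table 5-4 | Relation |
|---|---|---|---|
| Grade ≥2 pneumonitis | ends | delayed, then full dose and schedule (guideline) | opposite directions |
| PJP, any grade | ends | idelalisib stopped; no ofatumumab instruction in the text as read | unresolved |
| Organizing pneumonia, any grade | ends | as for PJP | unresolved |
| SJS/TEN, any grade | ends | idelalisib stopped; associated coadministered medications interrupted; ofatumumab not named | unresolved |

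Only the pneumonitis row is a direct conflict, because both columns of Table 5-4 are filled there.

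**2. Section 5.7 against itself.** Its main text ties ofatumumab to "a maximum of 12 infusions or the occurrence of any events requiring study drug discontinuation as defined in Section 5.8". Its note keeps Arm A on whichever drug was not stopped for toxicity. For a toxicity listed in Section 5.8, both cannot hold if *study drug* there means both drugs.

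**3. What *study drug* means**

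- *Idelalisib alone:* Section 5.3.4 uses it with the 150 mg and 100 mg BID dose levels. Section 9.4.1 lists study drug and ofatumumab as separate items. The idelalisib column of Table 5-4 uses it for Grade 1 pneumonitis.
- *Both drugs:* Section 2.1 and Section 5.4.1 each add a parenthesis naming idelalisib and ofatumumab.
- *Within Section 5.8:* the rechallenge bullet names idelalisib when only that drug is meant. The pregnancy bullet says *study drug*, and Section 5.4.11 shows that pregnancy stops both. The progression bullet must reach Arm B, which receives only ofatumumab.

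In Section 5.8 the two-drug reading therefore fits better, but the protocol as a whole does not fix the term.

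**4. Infusions that depend on the passage followed.** The schedule has 12 infusions: Weeks 1 to 8, then Weeks 12, 16, 20 and 24.

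- Arm B, Grade 2 pneumonitis after infusion 3: 12 − 3 = 9 remain. Sections 5.7/5.8 give 0; Table 5-4 allows up to 9.
- Arm A, Grade 2 pneumonitis at Week 10: infusions at Weeks 12, 16, 20 and 24 remain, which is 4. Sections 5.7/5.8 give 0; Table 5-4 gives 4 if none is lost to the delay.

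**The case against.** The best defence is that *study drug* in Section 5.8 simply means idelalisib, as in several other sections. The bullet would then match Table 5-4, Sections 5.4.2 and 5.4.9 and the Section 5.7 note, and the link from Section 5.7 to ofatumumab would still have content through progression, pregnancy and noncompliance. This reading is possible, so it is too strong to say that the term cannot mean idelalisib alone. It fits poorly, however, because the pregnancy and progression bullets use the same words for ofatumumab too and the rechallenge bullet names idelalisib.

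It is also fair that the ofatumumab entry for pneumonitis is not italicised. Section 5.3.4 makes such entries guidelines open to investigator judgment, and Section 5.8 says *should*. A site that stops ofatumumab may breach neither text. That softens the conflict, but the two passages still point in opposite directions.

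A reader might infer three further things that the documents do not support:

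- *That Table 5-4 continues ofatumumab after PJP, organizing pneumonia or SJS/TEN.* The first two rows show no ofatumumab instruction, perhaps because the cells are merged, and silence is not an instruction to continue. The SJS/TEN row could reach ofatumumab as a coadministered medication.
- *That bowel perforation is a further contradiction because Section 5.8 omits it.* Section 5.4.3 says idelalisib "must be discontinued in subjects who experience bowel perforation". The non-italic row for other Grade ≥3 events does not displace a *must*, and the Section 5.8 list is not exhaustive: PML (Section 5.4.8) is also absent.
- *That the PFS comparison is distorted.* No event rate is given, PFS is analysed by ITT (Section 9.3.1.1), and subjects who stop drug stay under assessment until progression (Sections 5.9 and 7.3).

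**Conclusion.** The point holds as an internal inconsistency. For Grade ≥2 pneumonitis the protocol gives opposite directions for ofatumumab, including in Arm B where it is the only drug, and Section 5.7 conflicts with its own note. For PJP, organizing pneumonia and SJS/TEN the finding is narrower: the undefined term leaves it open whether ofatumumab stops.

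The size for an affected subject is 0 versus up to 9 infusions in the Arm B example and 0 versus 4 in the Arm A example. These counts assume the planned schedule, no infusion lost to a delay, and an event judged treatment-related, since the title of Table 5-4 limits it to such events. How many subjects would be affected cannot be derived from the protocol. Safety, exposure and discontinuation counts are touched; an effect on PFS is not shown.

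**What to change.** Reconcile Sections 5.7, 5.8 and Table 5-4:

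- Define *study drug* in Section 5.8, or replace it in each bullet with the drug or drugs meant.
- For Grade ≥2 pneumonitis, PJP, organizing pneumonia and SJS/TEN, state for each arm which drug the rule applies to.
- Give an explicit ofatumumab entry in Table 5-4 for PJP, organizing pneumonia and SJS/TEN, and make the pneumonitis entry agree with Section 5.8.
- Word the Section 5.7 note and its link to Section 5.8 so that both can hold.

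Which clinical rule to adopt is the sponsor's decision; what is needed is that the passages agree. The cost is amendment wording, with no added procedures or subjects.

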### **5.9. Discontinuation from Study**

Subject study participation may be ended due to any of the following reasons:

- Disease progression (confirmed by the IRC)
- Withdrawal of consent
- Initiation of other anticancer therapy
- Physician's decision to remove the subject from the study
- Pregnancy
- The subject is lost to follow-up
- Death
- Discontinuation of study by the Sponsor, a Regulatory Agency, or an IRB or EC

Subjects who permanently discontinue study drug(s) for a reason other than disease progression (as determined by the IRC) shall continue with assessments per the schedule of procedures until disease progression or until study participation is ended.

### **5.10. Study Treatment Rationale**

Selection of the idelalisib treatment regimen (including starting dose level, dose-modifications and supportive care, schedule, duration, and conditions of administration) for this study has been based primarily on safety, exposure, and activity profiles from previous Phase 1 clinical studies involving healthy volunteers, patients with allergic rhinitis, and patients with refractory/relapsed lymphoid malignancies {[Coutre 2011](#), [Kahl 2011](#), [Webb 2010](#)}. The following information was considered in selecting the study drug dosing regimen for this study:

- Idelalisib was symptomatically well tolerated in patients with lymphoid malignancies receiving dose levels of 50 mg BID through 350 mg BID (the highest dose level tested). No specific MTD was apparent over the dose range tested. However, monitorable, reversible transaminase elevations were observed in some patients and may have been more frequent at higher dose levels (~10% rate among patients with CLL receiving starting doses of  $\geq 150$  mg). Thus, while doses through 350 mg BID appear tolerable, the starting dose of 150 mg BID appears to appropriately balance safety with efficacy in idelalisib-naïve subjects.

- In an allergic rhinitis study, idelalisib induced statistically significant improvements in clinical and pharmacodynamic endpoints when administered at 100 mg BID over 7 days. These data support the pharmacological relevance of idelalisib-mediated PI3K $\delta$  inhibition when administered at a dose-level approximating that to be used in this Phase 3 study.
- A positive correlation was noted between idelalisib dose and measures of tumor control and chemokine normalization in patients with B-cell malignancies. The majority of patients appear to have tumor responses and protracted PFS when receiving starting doses of  $\geq 100$  mg BID. Thus, treatment with a idelalisib at a starting dose of 150 mg BID appears to offer most patients the potential to benefit from therapy.
- Based on evaluations of idelalisib steady-state plasma  $C_{\max}$ , AUC, and  $C_{\text{trough}}$  values over a range of doses, administration of starting doses of idelalisib of  $\geq 150$  mg BID appears appropriate to ensure adequate exposure in the majority of patients. Flattening of the exposure curves at starting dose levels of  $> 150$  mg BID suggest that higher doses may achieve smaller incremental gains in exposure.
- In Phase 1 studies, the mean plasma  $t_{1/2}$  of idelalisib was  $\sim 6.5$  to 9.8 hours across all dose levels and there was no substantive plasma accumulation over 7 or 28 days. The collective data support a study drug administration schedule of BID administration to maintain idelalisib plasma  $C_{\text{trough}}$  values without inducing excessively high plasma  $C_{\max}$  values.
- The changes in exposure observed when administering idelalisib after a high-fat, high-calorie meal are modest ( $\sim 40\%$  increase in mean AUC with no change in mean  $C_{\max}$ ). Thus, idelalisib can be administered with or without food.
- The idelalisib dose modification provisions described in the protocol are designed to balance a primary concern for subject safety with the potential for observing pharmacological and antitumor activity in circumstances under which a subject experiencing an adverse event may still be able to continue on therapy at a lower idelalisib dose level. The enhanced monitoring to be performed and the actions to be taken in response to toxicity are based on experience with interruption, dose-modification, rechallenge, and re-escalation already piloted in idelalisib Phase 1 trials. In addition, idelalisib antitumor activity has been observed in the Phase 1 studies across all dose levels tested, including doses in the range of the modified dose levels planned for this protocol. Thus, use of the lower dose level to accommodate individual subject tolerability in this protocol is justified because subjects receiving such an idelalisib dose level still have the potential for benefit.
- Study treatment will be continued for each subject until the occurrence of disease progression. Such a strategy is considered appropriate under the assumption that persistent interference with PI3K $\delta$  signaling in Arm A is likely to extend treatment effect.

Use of ofatumumab in this study is based on product labeling, precedence established with ofatumumab and other monoclonal antibodies in patients with CLL, and clinical observations relating to coadministration of ofatumumab or other anti-CD20 antibodies with idelalisib:

- The ofatumumab dosing regimen (including the ofatumumab dose of 2000-mg/infusion) selected for the control arm (Arm B) of this study is the approved dose in product labeling {[Glaxo Group Limited 2011](#)}. Phase 1 pharmacodynamic data have suggested that this dose is appropriate to achieve CD20 target coverage when using ofatumumab as a single agent in patients with advanced, bulky lymphadenopathy {[Coiffier 2010](#)}.
- The ofatumumab dose of 1000 mg/infusion to be used in combination with idelalisib in the investigation arm (Arm A) of this study is supported by nonclinical and clinical data. Nonclinical data have indicated that exposure values consistent with a 1000-mg clinical dose are sufficient to provide saturation of the CD20 target {[Bleeker 2008](#)}. The findings of the Phase 1 pharmacodynamic study of ofatumumab suggest that this dose is appropriate in patients receiving concomitant therapy that could reduce tumor volume {[Coiffier 2010](#)}. Based on these collective results, current trials for patients with previously treated CLL use a 1000-mg dose of ofatumumab when giving the drug as a component of combination therapy. It is further conjectured that mobilization of CLL cells from sanctuary sites into the peripheral blood may enhance ofatumumab-mediated CLL cell killing. Additional benefits resulting from the lower ofatumumab dose may include reductions in the frequency and severity of ofatumumab-dependent infusion reactions and in the duration of ofatumumab administration.
- Administration of ofatumumab therapy for 24 weeks is consistent with recommendations in the ofatumumab package insert {[Glaxo Group Limited 2011](#)} and matches the total planned durations of drug administration typically employed with other antibodies (eg, alemtuzumab {[Keating 2002a](#)} or rituximab {[Robak 2010](#)}) used in the therapy of previously treated CLL.
- In a Phase 1/2, single-arm, dose-ranging study, concomitant administration of idelalisib at a dose of 150 mg BID together with ofatumumab at a dose of 1,000 mg has been shown to be safe and active {[Barrientos 2012](#), [Furman 2012](#)}.
- Consistent with the current product package insert for ofatumumab, subjects who are HBc antibody positive at screening will be monitored for HBV reactivation (manifest as detectable HBV DNA by quantitative PCR). Subjects will be tested monthly for the duration of ofatumumab therapy and every 3 months thereafter for 1 year from the end of therapy.
- Recommendations for managing ofatumumab infusion reactions, and interrupting or discontinuing ofatumumab therapy for specific adverse events are consistent with experience described in product labeling {[Glaxo Group Limited 2011](#)}.

## **6. STUDY PROCEDURES**

### **6.1. Enrollment and Study Management Procedures**

#### **6.1.1. Subject Recruitment**

Study candidates comprise subjects with CLL who are being followed at the specified study sites or are referred to the study sites. Subjects will be enrolled from investigational sites in the United States and other countries. The site principal investigator, designated sub-investigators, or other designees will discuss the possibility of participation directly with subjects who may be appropriate candidates for the study. The study sponsor will post a description of the study on the ClinicalTrials.gov website.

Promotional information generated by the sponsor or investigational sites will be submitted for IRB/IEC review, as required.

#### **6.1.2. Subject Compensation for Participation**

For subjects requesting such assistance, reasonable reimbursements for the costs of travel required to participate in this study will be provided by the study sponsor. To receive payment for travel, subjects will need to submit the original travel receipts to the research study staff at the investigational site.

However, other than medical care that may be provided, subjects will not be paid for participation in the study. Payments for such items as lost wages, disability, discomfort due to injury, or meals obtained while waiting at the clinical research center will not be provided. Through the informed consent process, study candidates will be notified that their insurance company could be charged for standard care that is a component of this research study and that subjects may be responsible for co-payments and deductible payments that are typical for their insurance coverage.

